Study treatments	
Test-Drug: Emodepside LSF oral solution (1 mg/mL) or matching placebo. Planned dose levels:
 
  
 Cohort	Dose level	Formulation	
   
 1	5 mg, OD, for 10 days	LSF oral solution (1 mg/mL)	
 
 2	10 mg, OD, for 10 days	LSF oral solution (1 mg/mL)	
 
 3	10 mg, BID, for 10 days (single dose on Day 9)	LSF oral solution (1 mg/mL)	
  
 
Emodepside administration will be given as fasted doses of LSF oral solution. Each morning dose will be given after an overnight fast of at least 9 h. On Days 0, 1, 8 and 9, subjects will fast until at least 4 h after dosing. On Days 2 to 7, subjects will fast until at least 1h after dosing. In Cohort 3, subjects will also fast for 2 h before and until 1 h after their evening dose.
 
Dose escalation will be decided by the Safety Review Group (SRG) at the Safety Review Meeting. The dose will not be escalated until the SRG have reviewed safety, tolerability and PK data until 48 h after the final dose of study medication in at least 4 subjects on active treatment (ie, at least 6 subjects overall), and agree that it is appropriate to give a higher dose; that decision will be taken in the Safety Review Meeting, before dosing of the subsequent cohort. The next planned dose level may be reduced, or a dose level may be re-tested or an intermediate dose level selected, based on emerging data.
 
The dose level will not exceed 20 mg LSF oral solution (1 mg/mL) per day.
 
If, within a treatment group, any of the following occurs, dose escalation will be stopped:
 
Safety stopping criteria
 
 There is 1 or more SAE, considered to be related to emodepside; 2 or more subjects in the same treatment group who present any severe or clinically significant AEs considered to be related to emodepside 
If a cohort fulfils a dose escalation stopping criterion, that dose level will not be repeated.
 
PK stopping criteria
 
 predicted mean plasma concentrations in the subjects at the next scheduled dose level exceed or equal: C_{max} 612 µg/L (based on the highest dose in the Single Ascending Dose (SAD) study DNDi-EMO-001)) 
The scheduled dose of emodepside may be reduced if, for example, the results of safety tests give any cause for concern, or tolerability is poor.
	Cohort	Dose level	Formulation	1	5 mg, OD, for 10 days	LSF oral solution (1 mg/mL)	2	10 mg, OD, for 10 days	LSF oral solution (1 mg/mL)	3	10 mg, BID, for 10 days (single dose on Day 9)	LSF oral solution (1 mg/mL)

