receiving placebo reported dry eye (n=1). All eye disorders AEs were of mild to moderate intensity, resolved spontaneously (without treatment), and were more frequently reported with highest dose (40 mg). Among them, the AEs of blurred vision, photophobia (“Increased ocular light sensitivity”), visual impairment (“distorted contrast perception”, “distorted colour perception”) reported by 8 out of 47 subjects receiving emodepside were considered as treatment-related by the Investigator. Also of note, at the highest dose (40 mg), lightheadedness (n=1), dizziness (n=1) or headache (n=1) were reported concomitantly to blurred vision.

None of the volunteers met any of the protocol-specified withdrawal criteria and overall tolerability to emodepside has been acceptable up to 20 mg. The presence of post-dose visual disturbances in subjects of Cohort 8 receiving either 40 mg solution or placebo may warrant some concern and escalation was stopped at this dose level.

The pharmacokinetic results obtained so far show that T_{max} for the LSF solution is consistently about 1 h post-dose when fasted. Mean C_{max} and AUC for the LSF solution have been roughly dose-proportional, with low to moderate inter-individual variability. The plasma half-life during the first 24 h is very short for a single dose of emodepside. After 3, 7, 16 and 47 h the maximum plasma concentration is reduced to 50%, 25%, 12.5% and 6.25% respectively. Terminal plasma half-life is 523 h. Although data of Cohort 9 (which was treated with a single dose of emodepside with food) are still under review, administration of the LSF of 10 mg with a high fat, high-calorie meal resulted in a clinically relevant food effect with a reduction of AUC to ~67%, C_{max} to 42% and a delay of the T_{max} up to 2.33 h. Therefore, the recommendation of administration of the emodepside (LSF) under fasted conditions is given.

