4.3. Dietary and lifestyle guidance

Subjects will abide by HMR house rules during the in-house period.

No food or drink containing grapefruit will be allowed from 7 days before dosing until after the Follow-Up Visit.

No alcoholic or caffeinated drinks, or smoking, will be allowed during the period from 24 h before admission until the end of each in-house period and for 24 h before each other visit including long-term follow-up visits. Subjects must not drink more than 3 units of alcohol daily at all other times during the study (1 unit = ½ pint of beer, 1 small glass of wine or 1 measure of spirits).

No strenuous exercise will be allowed from screening until after the Follow-up Visit, and from 48 h before each long-term follow-up visit.

Subjects should not expose themselves to sunlight for longer than 15 minutes without using a strong sunblock (factor (SPF) 30 or above), use a sunbed, or expose themselves to other sources of UV light (such as UV lighting in clubs), while taking the study medicine and until 3 days after their last dose

Standard meals will be provided at the usual times designated by the Investigator. Subjects will be allowed to drink water ad libitum at all times during the study.

Subjects should fast (no food or drink, except water) for 10 h before Screening Visit 1. During the in-house period (Days –3 to 14), subjects will fast on the following occasions:

- for at least 9 h overnight until the morning of Day –2, and until the OGTT has been administered;
- for at least 9 h before the morning of Day –1, and will have their first meal of the day after their morning assessments are complete.
- for at least 9 h overnight before their morning dose on Days 0–9, until 4 h after that dose on Days 0, 1, 8 and 9, and 1 h after the dose on other days;
- in Cohort 3, subjects will additionally fast for at least 2 h before and 1 h

after their evening dose on Days 0–9;

- for at least 9 h before their assessments on Day 10, 11, 12, 13, and 14, Day 23 outpatient visit, and the Follow-up (Day 30 \pm 2 days) and long-term follow-up visits (Day 60, 90 and 120 \pm 2 days).

On each occasion, subjects will be required to fast until scheduled assessments for the relevant time have been completed.

During the study (according to HMR procedures), and for 120 days after the subject's last dose of study medicine, subjects must not have sex without using a condom, unless they have had a vasectomy or their partner is not of childbearing potential.

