- Leptin and prolactin will also be measured at Screening Visit 1 and Day 9, as part of the insulin blood sample.
8. Administration of the study medicine will be done in fasting conditions on Days 0-9 at approximately the same time each morning (\pm 15 mins):
- in Cohorts 1 & 2, emodepside will be given in the morning only
 - in Cohort 3, emodepside will be given in the morning and evening (at 12 h intervals). On the last day (day 9), emodepside will be given only in the morning
9. 12-lead ECGs will be recorded in triplicate (with 1 minute between recordings) at -24 h (Day -1) before the morning dose on Days 0 and 9; single recordings will be made at all other time points. ECGs will be recorded:
- at Screening Visit 1 and at Follow-up (Day 30 \pm 2 days)
 - on Day -1: at -24, -23.5, -23, -22.5, -22, -21, -20, -16 and -12 h before the morning dose on Day 0
 - on Day 0: before and at 0.5, 1, 1.5, 2, 3, 4, 8 and 12 h after the morning dose
 - on Days 1-8: before the morning dose
 - on Day 9: before and at the following times after the morning dose: 0.5, 1, 1.5, 2, 3, 4, 8, 12, 24 (Day 10), 72 (Day 12) and 120 h (Day 14) after the Day 9 dose
- Subjects should rest in the supine position for 10 minutes before ECG measurements.
10. Vital signs will comprise blood pressure (BP) and heart rate (HR) at all time points, with oral temperature included at screening and -24 h before the morning dose on Day 0 (Day -1). Subjects should rest in the supine position for 10 minutes before single BP and HR measurements are taken. Vital signs will be measured:
- at the first screening visit and at Follow-up (Day 30 \pm 2 days)
 - on Day -1: at -24, -23.5, -23, -22.5, -22, -21, -20, -16 and -12 h before the morning dose on Day 0
 - on Day 0: before and at 0.5, 1, 1.5, 2, 3, 4, 8 and 12 h after the morning dose
 - on Days 1-8: before the morning dose
 - on Day 9: before and at the following times after the morning dose: 0.5, 1, 1.5, 2, 3, 4, 8, 12, 24, 36 (Day 10), 48 (Day 11), 72 (Day 12), 96 (Day 13) and 120 h (Day 14)
 - at outpatients visits on Days 17, 20, 23 and 27 (\pm 2 days), and long-term follow-up visits (Days 60, 90 and 120 \pm 2 days)
11. Adverse event monitoring will be done throughout the study, but scheduled questioning will be done at the following time points:
- at Screening Visit 1 and at Follow-up (Day 30 \pm 2 days)
 - on Day -1, at -24, -23, -22, -21, -20, -18, -16, -12 h before the morning dose on Day 0

Protocol Version/Date: Version 5, 25 July 2018

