7.1. Doses and treatment regimens

Randomised subjects will be given a unique ID (subject number; Table 6) that will be recorded in the case report form (CRF), and will be retained throughout the study.

This subject number will also appear on the study medication containers.

Table 6 . Study treatment: Subject numbers, Formulation, and Dose-Levels by Cohort

	Subject numbers ^a	Formulation and route of administration	Planned subjects	
			Emodepside	Matching placebo
Cohort 1	1001 – 1008	5 mg LSF solution OD, or placebo, by mouth	6	2
Cohort 2	2001 – 2008	10 mg LSF solution OD, or placebo, by mouth	6	2
Cohort 3	3001 – 3008	10 mg LSF solution BID, or placebo, by mouth	6	2

^a Any subjects who are replaced in a cohort will have the subject number incremented by 100 (eg, 1001 would be replaced by 1101)

Subjects will receive the study medication according to fasting instructions given in Section 4.3: On dosing days, following an 9 h overnight fast (no food or drink, except water), Investigator site personnel will administer study medication (active or placebo) to subjects with 240 mL ambient temperature water.

Subjects in Cohort 3 will be given an evening dose approximately 12 h after their morning dose on Days 0–9: they'll fast for 2 h before and 1 h after that evening dose.

Study treatment will be administered under the supervision of Investigator site personnel, following site standard procedures to ensure treatment compliance.

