8.2. Timing of Assessments

All procedures will be conducted according the Schedule of events, in Section 5.

General order of assessments

For the study periods described below, when multiple procedures are scheduled at the same time point(s) relative to dosing, the following chronology of events should

be adhered to, where possible:

- Neurological examination and physical examination
- 12-lead ECGs: after 10 minutes rest in the supine position single readings, with the exception of one triplicate reading
- Blood pressure/heart rate: after 10 minutes rest in the supine position
- AE monitoring (spontaneous and solicited AE monitoring will include specific questioning for tolerability and safety)
- PK blood sampling (taken at, or closest to, the nominal time point)
- PK blood sampling for metabolites
- Blood sampling for profiles of glucose, insulin, glucagon, and cortisol; single samples for prolactin and leptin; Laboratory safety blood samples. Urine samples will be collected when possible (dependent on the subject) but within the allowed deviation times.

Every effort should be made to ensure that protocol-required tests and procedures are completed as described. However, it is anticipated that from time to time there may be circumstances outside the control of the Investigator that may make it unfeasible to perform the test. In those cases, the Investigator must take all steps necessary to ensure the safety and well-being of the subject. When a protocol required test cannot be performed, the Investigator will document the reason for the missed test and any corrective and preventative actions which s/he has taken to ensure that required processes are adhered to as soon as possible. The Sponsor study team must be informed of these incidents in a timely manner. Allowable deviations for study assessments are detailed in Section 8.4 of this protocol.

To minimise variability, throughout the study, study staff should also ensure a minimum 10-minute supine period, where possible, before drawing any blood samples (including lab safety assessments).

Throughout the study (from subject signature of the ICF) AEs and concomitant medication will be documented as they are reported by the subjects. Subjects will also be questioned about AEs at the times that blood samples are taken, at follow-up, at long-term follow-up, and at the specific time points detailed in the Schedule of events (Section 5).

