8.3.8. Profile day (Day 9)

On the morning of Day 9, a cannula will be inserted into a forearm vein, under local anaesthesia with lidocaine 0.5%, for withdrawal of venous blood. The following will be done within 0.5 h before the morning dose of study medication and at the time points after administration outlined in the Schedule of Events (Section 5):

- Scheduled AE monitoring (particularly any event related to the CNS)
- Short neurological and physical examinations
- 12-lead ECGs (in triplicate only at the pre-dose measurement)
- Vital signs (BP and HR)
- Clinical safety laboratory evaluations (haematology, coagulation, biochemistry, urinalysis)
- Blood sampling to assay glucose, insulin, glucagon, cortisol
- Blood sampling to assay leptin and prolactin
- Blood sampling to assay pre-dose emodepside and its metabolites in plasma

Subjects in Cohort 3 will have a final morning dose of the study medication only on Day 9.

Subjects will fast overnight, as described in Section 4.3.

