1.2 AUC Calculations

The AUC will be calculated by a combination of linear and logarithmic methods. The linear trapezoidal method will be employed for all incremental trapezoids arising from increasing concentrations and the logarithmic trapezoidal method will be used for those arising from decreasing concentrations.

AUC_(0-∞) values with <20% of this area extrapolated will be reported.

It is acceptable to include data from profiles with >20% extrapolated as long as at least 80% of the profiles in the study have <20% of the AUC_(0-∞) as extrapolated area. In this instance, individual plasma concentration-time profiles for which the extrapolated areas are >20% of AUC_(0-∞) will be identified.

It is unacceptable to use AUC_(0-∞) data if >40% of the AUC has been extrapolated, except in specific situations which should be carefully justified in the study report.

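### Protocol 7.1 and 4.3 carry the Cohort 3 evening dose through Day 9, while every day-specific instruction gives the morning dose only on that day.

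*Protocol*

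**What the plan says.** Two places carry the Cohort 3 evening dose through Day 9:

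- Protocol 7.1 (Doses and treatment regimens): "Subjects in Cohort 3 will be given an evening dose approximately 12 h after their morning dose on Days 0–9".
- Protocol 4.3 (Dietary and lifestyle guidance): Cohort 3 fasts for at least 2 h before and 1 h "after their evening dose on Days 0–9".

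Four places exclude it on Day 9:

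- Protocol summary, Study treatments table: "10 mg, BID, for 10 days (single dose on Day 9". This does not use the word morning, but it rules out a second dose.
- Protocol 5.1, schedule footnote 8, attached to the row for emodepside administration: "On the last day (day 9), emodepside will be given only in the morning".
- Protocol 8.3.8 (Profile day, Day 9): "Subjects in Cohort 3 will have a final morning dose of the study medication only on Day 9".
- SAP schedule of events, footnote 8: the same statement as in the protocol.

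Protocol 8.2 adds: "All procedures will be conducted according the Schedule of events, in Section 5". Sections 3.2, the introduction to Section 7 and Table 6 describe Cohort 3 as twice daily without mentioning Day 9.

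**The concern.** The two sets of statements cannot both be followed. Giving a Day 9 evening dose departs from 8.3.8, and withholding it departs from 7.1. SAP 13.2 counts an incorrect dose as a major protocol deviation. The error sits in the section that defines the regimen, and 7.1 sends the reader for fasting rules to 4.3, which repeats it.

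What is at stake is the Cohort 3 Day 9 profile. Plasma sampling continues after 12 h (15, 24, 36 and 48 h, and on to Day 30), with every time counted from the morning dose. A dose at 12 h would mean that all those later samples follow two doses. AUC-infinity is a main Cohort 3 parameter. AUClast and MRT are exploratory, and the dominant half-life is defined on the 0–24 h curve. Any optional 12–24 h urine collection would also be affected, and the 24 h assessments on Day 10 would fall 24 − 12 = 12 h after the last dose.

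**Working it through.** **Dose count.** Morning only on Day 9: 9 days × 2 + 1 = 19 doses, 190 mg. As 7.1 is written: 10 days × 2 = 20 doses, 200 mg. The difference is one 10 mg dose for each of the six planned active subjects. The Day 9 total would be 20 mg, equal to the cap and to the total on each earlier dosing day.

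**Parameters that do not change.** AUC12 and RA(AUC) use only 0–12 h. Ctrough comes from pre-dose samples on Days 1–9, all before the extra dose. Cmax,ss and RA(Cmax) change only if a sample after 12 h exceeds the morning peak, and the next sample is at 15 h. All this requires the 12 h sample to precede the dose.

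**Illustrative size.** Inputs from Protocol 1.4: tmax about 1 h; decline to 50, 25, 12.5 and 6.25% of peak at 3, 7, 16 and 47 h; terminal half-life 523 h; a high-fat meal that "resulted in a clinically relevant food effect with a reduction of AUC to ~67"%. Assumptions:

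- Kinetics are linear.
- The unit curve f rises linearly to 1 at 1 h, then is log-linear through the four decline points. These are timed from dose or from peak, because the protocol does not say which.
- Beyond 47 h, f(t) = s·2^(−(t−47)/523) + (0.0625−s)·2^(−(t−47)/31). Here s is the share of peak that follows the 523 h phase, and 31 h is the half-life implied by the last two points (47 − 16). The documents do not give s; it is varied from 0.5% to 6.25%.
- Evening doses are scaled by F, from 0.67 to 1. The fed figure serves as a lower bound because evening doses follow a 2 h fast.

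At u hours after the Day 9 morning dose, with d the dosing day:

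C(u) = Σ(d=0..9) f(u+24(9−d)) + F·Σ(d=0..8) f(u+24(9−d)−12)

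The extra dose adds F·f(u−12).

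Worked values at 15 h, in units of the single-dose peak:

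- Dose-timed, s = 6.25%, F = 0.67: C = 1.013; extra = 0.67 × 0.5 = 0.335; ratio 1.348/1.013 = 1.33.
- Dose-timed, s = 6.25%, F = 1: C = 1.193; extra = 0.5; ratio 1.693/1.193 = 1.42.
- Peak-timed, s = 0.5%, F = 1: C = 0.618; extra = 0.5^(2/3) = 0.630; ratio 1.248/0.618 = 2.02.

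Ranges over both timings and F = 0.67 and 1:

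| s (share of peak) | Rise at 15 h | Rise in AUC-infinity | AUC-infinity extrapolated from Day 30 (no extra dose) |
|---|---|---|---|
| 6.25% | 33–52% | 5.2–6.6% | 51% |
| 2% | 52–82% | 6.7–8.7% | 46–47% |
| 1% | 60–94% | 8.5–11.1% | 41% |
| 0.5% | 65–102% | 11.1–14.6% | 33–34% |

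In every case the AUC 0–12 h ratio is 1.000. With the extra dose the 15 h concentration is 0.56–0.84 of the Day 9 morning peak, so observed Cmax,ss is not displaced. The half-life fitted over Days 17–30 changes by less than 5% (for example 410 to 392 h at s = 0.5%, peak-timed, F = 1).

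**The case against.** The strongest reply is that nobody would be misled. The day-specific instructions agree: footnote 8 belongs to the drug-administration row, 8.3.8 is the instruction for that visit, and 8.2 points procedures to the schedule. Sections 7.1 and 4.3 are range statements that omit an exception. Site staff supervise dosing, from individually dispensed containers. Even if an evening dose were given, the daily cap would hold and most main Cohort 3 parameters would survive.

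Most of this stands. It settles what is intended and keeps the severity low. It does not make 7.1 correct. Section 8.2 is headed as timing of assessments, and no text says that the schedule overrides the regimen section on dosing.

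A second objection also stands: the percentages do not come from the documents. Protocol 1.4 gives a 47 h level and a terminal half-life separately and does not say how much of that level belongs to the slow phase. The 40 mg figures do not settle it: 4,315/612 = 7.05 h, but the type of AUC is not stated. The unit curve gives about 55 h to infinity at s = 6.25% (dose-timed) and only about 7.8 h up to 47 h. A smaller share makes the conditional distortion larger.

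**Conclusion.** The contradiction is in the current protocol text and does not depend on any model. Sections 7.1 and 4.3 are wrong as written, and morning only on Day 9 is intended. If 7.1 were followed, the effect would be one extra 10 mg dose per active Cohort 3 subject and a distorted profile after 12 h. Under linear superposition, with terminal shares of 0.5–6.25% of peak and evening absorption of 67–100%, the 15 h concentration would rise by about 33–100% and AUC-infinity by about 5–15%. These figures are illustrative.

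Three stronger readings are not supported:

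- A reader might infer a safety breach. The Day 9 total would stay at 20 mg.
- A reader might infer that a dosing error is likely. The Pharmacy Manual and the expanded Day 9 schedule are not available here, so that cannot be judged.
- A reader might infer that AUC-infinity is unusable in any case, since the SAP rules it out "if >40% of the AUC has been extrapolated, except in specific situations which should be carefully justified in the study report". The modelled extrapolated share runs from about 51% down to 33% as the assumed terminal share falls, so the documents do not place it above that limit.

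Severity: minor to should-fix.

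**What to change.** In Protocol 7.1 and in the Cohort 3 evening-dose bullet of 4.3, change Days 0–9 to Days 0–8. Leave the morning-dose fasting rule in 4.3 at Days 0–9. Optionally, note the Day 9 exception in Section 3.2, the introduction to Section 7 and Table 6. The SAP needs no change.

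The cost is two wording edits in an amendment approved and signed by the sponsor and principal investigator. Under Protocol Section 13, REC approval (and regulator approval, if applicable) is needed before implementation unless the change is treated as administrative. No subjects, samples or assessments are added.

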7.2. Emodepside study treatment

Detailed information on the drug substance emodepside (BAY 44–4400) is given in the Investigator's Brochure.

The study treatment will be provided as 0.1% (w/v) emodepside oral (LSF) solution with 1 mg active pharmaceutical ingredient (emodepside, BAY 44-4400) per mL. It is available as bulk solution in a brown glass container with a dosing adapter and child-resistant screw cap closure.

Doses up to 20 mg, corresponding to 20 mL solution, can be dispensed from 1 bottle. The solution has to be withdrawn from the container using a syringe and is then administered directly from the syringe into the mouth of the subject. The solution should not be diluted before application. The solution may be used for application of doses up to a maximum of 20 mg per day corresponding to application of 20 mL of the solution per day, based on the results of the single-administration dose study (DNDI-EMO-001).

The solution is composed of the active substance emodepside and the following excipients:

- macrogol 400
- polysorbate 20
- levomenthol
- butylhydroxyanisole.

